Previous studies have reported 3-30% parasite prevalence in asymptomatic refugees from malaria endemic areas [11-14]. In Sweden, health screening is offered to newly arrived immigrants, including HIV, tuberculosis and viral hepatitis. Currently, malaria is not included in the screening program in

Sweden, although other countries recommend screening [15-17] and in the US, presumptive treatment is offered without testing [18]. Neither is there any regular testing for other parasites, not even preceding long term corticosteroid treatment.

Moreover, duration of asymptomatic parasite carriage in non-endemic countries is not fully established, however, case reports suggest that infections may persist for several years [20].

The immunologic response to malaria infection consists largely of antibodies towards a variety of parasite antigens, and develops over the course of several symptomatic malaria infections [22]. In highly endemic areas, immunity gradually protects against the severe forms of the disease and on further exposure, protection against clinical symptoms evolves [4, 22]. However, the protective immunity wanes over time with ceased exposure and thus previously protected individuals living in non-endemic countries are at risk for developing a more severe disease upon re-exposure for example when travelling to visit friends and relatives [23]. The longevity of circulating antibodies towards malaria is not fully elucidated, and therefore the risk cannot be fully appreciated.

This project focuses on the burden of malaria and other parasitic infections in newly arrived migrants and immigrants with longer residency in Sweden. We will evaluate the parasite prevalence and if screening for malaria and other parasites should be offered in migrants from Sub-Saharan Africa. In addition, we will assess longevity of malaria-specific immune responses as well as how migrants navigate through the Swedish health system.

Study design: Cross-sectional observational study.

Study population:

1. Newly arrived migrants born in countries where malaria is endemic (ie Sub-Saharan Africa) will be invited to participate in the study at migration health care units in Stockholm and Västerås. Blood samples will be collected at the time of routine sampling. According to sample size calculation based on expected 5% prevalence (see below) a total of 715 individuals will then be included in total. This number will be adjusted based on results in the pilot study.

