2. Immigrants from malaria endemic countries living in Sweden will be invited to participate with voluntary blood sampling on one occasion. The study will be advertised in posters in waiting areas at health clinics in Stockholm.
3. Letter invitations to individuals arriving in Sweden from Democratic Republic of the Congo and Uganda between 2015 and 2019 and with a postal address in the Stockholm County, will be sent an invitation letter offering to participate in the study.

Inclusion criteria: Born in a malaria endemic country, defined as a country with indigenous spread of malaria reported in the World Malaria Report (WHO) 2019.

Exclusion criteria: Inability to understand patient study information or inability sign the informed consent form, with exception to children under 15 where legal guardian may approve and sign consent.

Sampling and analyses: A venous blood samples (EDTA tube) will be collected on one occasion. To minimize the amount of venipunctures and time for the study participants, blood samples will be collected on the same occasion as other blood samples taken within the routine screening program for newly arrived migrants. A short questionnaire including questions about patient origin and previous malaria as well as other diseases and previous treatment will be completed at the time of sampling with the aid of a translator if needed.

Blood samples will be sent to the research laboratory for malaria diagnostics and haemoglobin concentration. A rapid diagnostic test (RDT) will be performed for malaria. The sample will thereafter be centrifuged, aliquoted, and stored frozen at the research laboratory. Presence of parasites will be analysed by realtime-PCR of the species specific 18SRNA gene in a multiplex assay [25]. In study population 4, malaria microscopy will be performed at the same time as RDT to increase sensitivity.

RDT is less sensitive than microscopy and PCR but offers a rapid result, the same day with this set up, and all positive individuals will be referred to the Department of Infectious Diseases at the regional hospital for further investigations and treatment. Likewise, all individuals found to be positive for malaria by microscopy and/or PCR at a later stage will be contacted and referred for complete assessment and treatment at the Department of Infectious Diseases. Results from complete blood count will be assessed and followed up according to clinical routine at each centre where samples were collected.

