Contact information to the study participant will be included as part of the recruitment and consent procedures in order to be able to contact the study participants for referral.

Complementary to the proposed study, health economic aspects of malaria screening will be assessed for cost-effectiveness estimation.

Moreover, PBMC will be prepared from a subset of patients to assess the cellular immune response. Plasma samples will be analyzed for the presence and levels of antibodies against crude whole *P. falciparum* parasite extract using ELISA, and against a panel of specific pre-hepatic and blood stage antigens using a multiplex Luminex [26]. The magnitude and breadth of antibody responses will be related to duration of residency in a malaria free country. This will allow us to estimate the long-term decay kinetics using a sero-epidemiological mathematical model [27]. In addition, serological markers for schistosomiasis and strongyloides will be analysed at the Public Health Agency of Sweden.

A subset of volunteers among immigrants living in Sweden (n=100) will be asked to contribute with a second blood sample after 6-12 months. This will allow us to estimate the long-term decay kinetics using a sero-epidemiological mathematical model [27].

Statistical analysis

The analyses will be performed using Stata version 14.2 (StataCorp, College Station, TX, USA). Categorical variables will be summarized by proportions, and the numerical variables by medians and interquartile ranges (IQR). In comparative analyses, categorical variables will be analyzed using the Pearson's chi-squared test, or the Fisher's exact test when appropriate. The Mann-Whitney's U-test will be used for comparing the distribution of numeric variables between two groups and the Kruskal-Wallis's test among multiple groups. Backward stepwise univariable logistic regression will be used to potential risk factors for parasitic infection. The variables with a p-value less than 0.05 will be

kept in the final multivariable model. The Wald's test will be used to test the regression coefficients. P-values less than 0.05 were considered statistically significant.

Significance

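### The risk-factor rule asks for backward elimination in a univariable model, so the plan's only adjusted analysis of infection has no single reading

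*Combined protocol and SAP*

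**What the plan says.** In the combined protocol and SAP, the Statistical analysis section describes the risk-factor analysis in three sentences. The first reads "Backward stepwise univariable logistic regression will be used to potential risk factors for parasitic infection". The second, broken by a page change, reads "The variables with a p-value less than 0.05 will be" and continues "kept in the final multivariable model". The third adds "The Wald's test will be used to test the regression coefficients". A general significance level of 0.05 follows.

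The other comparisons in that section are unadjusted: "In comparative analyses, categorical variables will be analyzed using the Pearson's chi-squared test, or the Fisher's exact test when appropriate", with rank tests for numeric variables. The only other model in the plan concerns antibody decay.

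The outcome is called parasitic infection without further definition. Malaria is diagnosed by rapid test and PCR, and under Sampling and analyses "serological markers for schistosomiasis and strongyloides will be analysed at the Public Health Agency of Sweden". The analysis population is not named. Newly arrived migrants are recruited at migration health units, settled immigrants by poster, and a third group by post: "Letter invitations to individuals arriving in Sweden from Democratic Republic of the Congo and Uganda between 2015 and 2019". The questionnaire topics are listed, but not the candidate variables for the model. For newly arrived migrants the size is given as follows: "According to sample size calculation based on expected 5% prevalence (see below) a total of 715 individuals will then be included in total".

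**The concern.** Backward elimination starts from a model with several covariates and removes them one at a time. A univariable model has one covariate, so the named procedure cannot be run. Either univariable is a slip for multivariable, or a screening step has been run together with an elimination step. The text does not settle which, and it does not say whether the 0.05 threshold applies to the unadjusted or the adjusted p-value.

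Two competent analysts could therefore report different risk factors from the same data. Under either reading, a place in the final model depends only on p below 0.05. With few infections, a weak factor that passes such a threshold tends to look stronger than it is. At stake is the only adjusted description of who is infected.

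**Working it through.** **Inputs from the plan.** n = 715 and 5% expected prevalence (Study population, group 1); 3–30% prevalence in earlier studies (Background); p < 0.05 for retention and Wald tests (Statistical analysis). The figure 715 is used here only as an input. The formula n = z²p(1−p)/d² with p = 0.05, z = 1.96 and d = 0.016 gives 713. That half-width is inferred, not stated, so 715 is neither confirmed nor disputed.

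**Step 1, expected malaria cases in newly arrived migrants.** 715 × 0.05 = 35.75, about 36. Over the cited range: 715 × 0.03 = 21.5 and 715 × 0.30 = 214.5.

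**Step 2, do the readings differ?** Assumptions for the simulation: five binary candidates, each at 30% frequency, with true odds ratios 1.5, 2.0, 1, 1 and 1. Reading A enters every variable with univariable p < 0.05 into one model. Reading B eliminates backward at p < 0.05 from all five. The final models can be compared in two ways: by which variables they contain, and by which of those are significant in them. The second matters because, under A, a variable can enter on its unadjusted p-value and then be non-significant after adjustment.

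| Share of studies in which A and B differ, 5% prevalence | Independent | Correlation about 0.18 | Correlation 0.32 |
|---|---|---|---|
| Variables in the final model | about 5% | about 30% | about 50% |
| Variables significant in the final model | about 3% | about 11% | about 22% |

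The difference in membership at 3% and 30% prevalence is 3% and 10% (independent), 19% and 63% (0.18), and 35% and 92% (0.32). At 30% prevalence and correlation 0.32, the significant variables differ in 23%. A third reading, a screen followed by elimination, differs from B in 2–6% of studies. A separate set-up with 8 or 12 correlated candidates, two of them true factors, gave different membership in 35–44% of runs at odds ratio 1.5 and 69–78% at 2.0.

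**Step 3, null factors (5% prevalence, correlation 0.32).** At least one null factor is in the final model in about 40% of studies under A and 20% under B. At least one is significant there in about 10% under A and 20% under B.

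**Step 4, inflation for a true odds ratio of 1.5 (independent candidates).** Each cell gives the share of studies, the median estimate and the coverage of the 95% interval.

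| Prevalence | Kept by backward elimination | Significant in the unselected full model | All full-model estimates |
|---|---|---|---|
| 3% | 15.0%, 2.86, 84% | 14.8%, 2.92, 82% | 100%, 1.51, 95% |
| 5% | 21.5%, 2.34, 88% | 21.7%, 2.34, 88% | 100%, 1.51, 95.5% |
| 30% | 63.8%, 1.65, 96% | 63.8%, 1.65, 96% | 100%, 1.51, 95% |

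At correlation 0.32 and 5% prevalence the medians are again close (2.56 by elimination, 2.59 for significant full-model factors), but coverage is 77% against 86%. Over all full-model estimates the median is 1.49 and coverage 96%.

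**Step 5, precision of a full model.** For a 30% factor at odds ratio 1 and 35.75 cases, the expected cell counts are 10.725 and 25.025 infected, and 203.775 and 475.475 uninfected. SE = √(1/10.725 + 1/25.025 + 1/203.775 + 1/475.475) = 0.374, and exp(1.96 × 0.374) = 2.08. The 95% interval runs from about OR/2.1 to OR × 2.1. The factor is 2.55 at 21.5 cases and 1.42 at 214.5.

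**Step 6, sparse categories (36 cases, assumed group sizes).** For 0/100 against 36/615 the Wald p is about 1, Firth 0.005 and Fisher 0.006. For 1/100 against 35/615 Wald gives 0.080 and Firth 0.039. For 2/100 against 34/615 both give 0.15. For 0/60 Firth gives 0.052.

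**The case against.** The strongest reply is that the size depends on what is counted. The plan goes on to test the coefficients, so a factor that enters under A but is non-significant after adjustment need not be read as a finding. Counted by significance in the final model, the disagreement falls by roughly half or more. A reader might also infer that reading A produces many more false risk factors; that holds for membership only and reverses for significance. This objection stands, which is why both counts are given. What remains is material only if candidates are correlated, and every correlation here is assumed.

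Three further inferences are tempting, and the documents do not support them.

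- **That non-significant estimates will be hidden.** The plan says which variables stay in the final model. It does not say that other estimates will be withheld, and reading A yields a univariable estimate for every candidate.
- **That elimination itself causes the inflation.** Significant factors in an unselected model are inflated to a similar degree. The argument is for reporting everything.
- **That the first aim fails.** Prevalence by origin, with proportions and chi-squared or Fisher tests, addresses it without this model. Risk-factor modelling is in neither specific aim.

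The Wald point is also narrow. It is decisive only for a category with no infected people in a fairly large group, and the plan does not say that origin will be entered as categories. The unnamed outcome, population and candidates are mostly missing detail. Finally, simply choosing one procedure would remove the contradiction. That is true, but it would leave p below 0.05 as the only criterion for a place in the final model.

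**Conclusion.** The contradiction is in the text and nothing elsewhere resolves it. It should be fixed, because it governs the only adjusted analysis of infection. At 5% prevalence the two readings give final models with different variables in about 5% to 50% of studies, and different significant variables in about 3% to 22%, as the correlation between candidates rises from 0 to 0.32. At about 36 cases, a true odds ratio of 1.5 that survives backward elimination has a median estimate of about 2.3, against about 1.5 over all full-model estimates. At 30% prevalence that inflation is small, but the readings still diverge when candidates are correlated.

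These sizes rest on assumed numbers, frequencies, effects and correlations of candidates, because the plan lists none. The textual contradiction rests on no assumption. Prevalence estimates and unadjusted comparisons are untouched.

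**What to change.** Replace the two sentences on stepwise selection with:

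> Risk factors will be assessed with one multivariable logistic model per infection outcome (PCR-positive malaria; schistosoma serology and strongyloides serology where tested), separately by recruitment population, with newly arrived migrants as the main population. Candidate variables will be fixed before analysis from the questionnaire, their number limited by the expected number of infections (about 36 for malaria at 5%). No variable will be added or removed by p-value; all adjusted odds ratios with 95% CIs will be reported, and results are exploratory.

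The candidate list itself should be written down before the data are analysed; otherwise two analysts could still differ.

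Optional: where a category has no infected people, use Firth or exact logistic regression instead of the Wald test, after checking that the planned Stata version offers it. In small groups (about 60 or fewer at 36 cases) Firth still does not reach p < 0.05; the gain there is a finite estimate and interval.

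The cost is wording and a little analysis time, with no new data. The downside is a less parsimonious model and openly wide intervals: about OR/2.1 to OR × 2.1 for a 30% factor at 36 cases.

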Study protocol

Infections in migrants: the importance of malaria and other parasites

2021-08-01

Study protocol

Infections in migrants: the importance of malaria and other parasites

Overall aim

The purpose of this project is to improve the health in migrants and immigrants focusing on malaria and other parasitic infections.

Specific aims

1. To assess the parasite prevalence in newly arrived migrants and the need to introduce screening for malaria and other parasites in migrants from certain countries.
2. To assess the parasite prevalence and specific antibody responses to malaria and other parasitic infections in immigrants who live in Sweden.

Background

Malaria is a major threat to human health, especially in Sub-Saharan Africa [1]. Global migration has resulted in a surge of refugees and asylum applications in Europe, many from malaria endemic countries.

The symptoms of malaria range from mild febrile illness to life-threatening multi-organ failure [3]. Disease severity is influenced by several host-parasite interactions, where host immunity is believed to be one of the most important [4].

Immunity to malaria is gradually acquired after repeated infections in populations living in high-endemic areas [4]. However, sterilizing immunity does not seem to evolve, and asymptomatic low-level infections are common. Individuals may carry a low grade parasitemia for extended periods of time [5]. Chronic parasitemia may lead to anaemia [6], cognitive dysfunction [7], adverse events during pregnancy [8] and may have hidden cost on telomere degradation and ageing [9].

Migrants from malaria endemic areas may present with febrile malaria but may also harbour asymptomatic malaria infection. Moreover, other parasitic infection can cause silent infections with adverse effect on health, such as schistosomiasis causing bladder calcification and strongyloides that may progress to a life-threatening disease called strongyloides hyperinfection, especially in patients receiving corticosteroids or other immunomodulatory treatment.

Thus, estimating the burden of malaria and other parasitic infections in newly arrived migrants as well as in immigrants with longer residency in Sweden is important in order to improve health in these populations.

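### The Wald test in the risk-factor model cannot recognise a category with no infections, and loses power for sparse low-risk categories

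*Combined protocol and SAP*

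**What the plan says.** The Statistical analysis section sets out the regression in a few sentences. The model is introduced with "Backward stepwise univariable logistic regression will be used to potential risk factors for parasitic infection". Retention follows from a sentence that begins "The variables with a p-value less than 0.05 will be" and goes on to say that such variables stay in the final model. The test is given by "The Wald's test will be used to test the regression coefficients", and the general threshold by "P-values less than 0.05 were considered statistically significant".

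No likelihood-ratio, exact or penalised method is named for the regression, and there is no rule for sparse categories. Fisher's exact test is planned, but only for the comparative analyses of categorical variables. Candidate factors and their categories are not listed.

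The only figures that bear on the number of infections are in Study population, item 1: "sample size calculation based on expected 5% prevalence (see below) a total of 715 individuals". That size is provisional: "This number will be adjusted based on results in the pilot study". The Background cites earlier prevalences of 3-30%.

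**The concern.** Specific aim 1 includes assessing "the need to introduce screening for malaria and other parasites in migrants from certain countries". Country or region of origin is therefore a natural candidate factor, and the questionnaire collects it. A category in which almost nobody is infected is informative for that aim, because it points to people who may not need screening.

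The Wald test behaves badly in exactly that situation. It divides the estimated coefficient by its standard error. As the infections in a category fall to zero, the standard error grows faster than the coefficient, so the evidence appears to weaken as it becomes stronger. Under a p<0.05 retention rule, the adjusted model may then say nothing about a group that the unadjusted table shows to be at clearly lower risk. The plan has no rule for resolving that conflict.

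**Working it through.** **The plan's own figure.** The 715 cannot be reproduced, because the documents give no precision, margin or power. A half-width of 1.6 percentage points gives 1.96² × 0.05 × 0.95 / 0.016² = 713, but that half-width is back-solved. I take 715 and 5% as given.

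**Inputs.** Expected infections are 715 × 0.05 = 35.75, about 36. At 3% and 30% they would be about 21 and 215. From the plan: Wald test, p<0.05 (taken as two-sided). My assumptions: newly arrived migrants only, one binary factor, and the group sizes and true prevalences below.

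**Zero infections: 0/100 against 36/615.** The log odds ratio is ln[(0 × 579)/(100 × 36)], which is minus infinity. Iterative fitting shows what the Wald test does:

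| Iterations | Coefficient | Standard error | Wald p |
|---|---|---|---|
| 8 | -6.79 | 7.25 | 0.35 |
| 15 | -13.79 | 240 | 0.95 |
| 25 | -23.79 | 35,612 | 0.999 |

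On the same data the ordinary likelihood-ratio test gives p=0.0008, Firth's penalised likelihood-ratio test p=0.005 and Fisher's test p=0.006. With 36 infections in 715 and none in the group, the likelihood-ratio test is significant from 37 people and Fisher from 67. Wald is not significant at any size.

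**One infection: 1/100 against 35/615.** The log odds ratio is ln[(1 × 580)/(99 × 35)] = -1.79 (odds ratio 0.17). Its standard error is √(1/1 + 1/99 + 1/35 + 1/580) = 1.02, so z = -1.75 and Wald p=0.080. Firth gives 0.039 and Fisher 0.047. The estimate is finite, and Wald recovers as the group grows: p=0.049 at 1/120, 0.029 at 1/143 and 0.009 at 1/200. With exactly one infection, Wald misses what the ordinary likelihood-ratio test finds only for groups of 82 to 119 people.

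**Power.** I enumerated two binomials exactly, holding overall prevalence at 5%, so that prevalence elsewhere is (35.75 - m × p)/(715 - m) for a group of size m and true prevalence p. A zero-infection group counts as Wald p=1.

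| Group size | True prevalence | Wald | Firth |
|---|---|---|---|
| 100 | 1% | 4% | 59% |
| 100 | 0.5% | 3% | 79% |
| 150 | 1% | 55% | 86% |
| 200 | 1% | 81% | 96% |
| 200 | 0.2% | 33% | over 99% |

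The last two rows show the reversal: at fixed size, Wald power falls as the group gets closer to infection-free. The reason is that power cannot exceed the chance of seeing at least one infection, 1 - (1 - p)^m. At size 200 and 0.2% this is 1 - 0.998^200 = 1 - 0.670 = 33%, the figure in the table.

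**Raised risk.** For a group of 100 at 10%, Wald and Firth each have 63% power; at 15%, each has 98%.

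**Choice of replacement.** With no true difference (5% in both groups), type I error at size 100 is 3.1% for Wald, 5.5% for the ordinary likelihood-ratio test and 4.7% for Firth. At size 40 the ordinary likelihood-ratio test reaches 9.7%.

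**The case against.** A reader might infer more than the documents support, in five respects.

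- *That the test also breaks down with one infection.* It does not; it is conservative there and works from about 120 people.
- *That sparse categories are certain to arise.* The documents give no categories or sizes, so this is an assumption. It is a plausible one: at 1% true prevalence the chance of no infections is 0.99^100 = 37% in a group of 100 and 0.99^200 = 13% in a group of 200.
- *That a low-risk group will always be discarded.* Retention applies to variables. An origin variable with 0/100, 10/265, 8/200 and 18/150 infected has a joint Wald p of about 0.006 on 3 degrees of freedom, counting the empty level as contributing nothing. The variable stays, although the empty level still has no usable coefficient or Wald interval.
- *That the model will have 36 infections.* The modelled outcome is parasitic infection, which may include schistosomiasis and strongyloides. The other two study populations have no stated size, and the 715 may change. More infections overall do not, however, repair a category that has none.
- *That aim 1 cannot be answered.* The plan reports proportions and uses Fisher's test where appropriate, and Fisher is significant in both worked examples. Nothing makes a regression p-value the basis for sparing a group from screening.

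These limits stand and narrow the point. They do not remove it: the one test named for the adjusted model cannot respond to the strongest evidence of low risk. It is also fair to say that Firth throughout is not essential. At sizes 100 and 150 the ordinary likelihood-ratio test has type I error of 5.5% and 5.3%, and more power at 1% true prevalence (72% against 59%, and 90% against 86%).

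**Conclusion.** The point holds for sparse, low-risk categories in the adjusted model. With no infections in a category, the Wald test is uninformative at any group size, or the category and its people are omitted; Stata's behaviour was not tested here. With one or two infections it loses power, heavily in groups of around 100 and much less in groups of 200 at 1% true prevalence.

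The sizes quoted rest on 715 people, 5% prevalence, a single binary factor and assumed group sizes. They also take the retention p-values to be Wald p-values, the only regression test named. Prevalence estimates, unadjusted comparisons and factors that raise risk are not affected. The change is worth making because the stated rule performs worst where the adjusted model could best identify people at low risk.

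**What to change.** Replace the Wald sentence with wording such as: *Variables will be retained on likelihood-ratio tests. Where any category has no or very few infections, the model will be fitted by Firth penalised logistic regression, with penalised likelihood-ratio tests and profile penalised-likelihood 95% confidence intervals; such categories and their participants stay in the model.* State in advance the number that counts as very few. Models compared by a likelihood-ratio test must be fitted to the same people, so silent omission of an empty category has to be prevented. Using Firth throughout is also acceptable and avoids having two methods.

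The cost is a short edit to the Statistical analysis section and an add-on command for Stata. Odds ratios are shrunk slightly towards 1 under the penalty. No new data are needed.
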